### **9.3.2.3        Quality of Life**

Quality of life is assessed via the EQ-5D. The EQ-5D consists of the EQ-5D descriptive system and the EQ visual analogue scale. The EQ-5D descriptive system includes 5 dimensions: mobility, self-care, usual activities, pain/discomfort and anxiety/depression. The response for each of the dimensions is ordered categorical: 1 = no problems, 2 = slight problems, 3 = moderate problems, 4 = severe problems and 5 = unable to/extreme problems. The EQ-5D domains will be summarized descriptively in terms of the percent of subjects falling into each ordered category at any given timepoint; the data will also be explored by cumulative and adjacent logit analyses.

The EQ visual analogue scale records the respondent’s self-rated health on a vertical, visual analogue scale where the extremes are ‘100 = Best imaginable health state’ and ‘0 = Worst imaginable health state’. The change in visual analog scale score from baseline to any given time point will be summarized descriptively.

### **9.3.3        Safety Analysis**

All subjects who receive any dose (any amount) of MT-3724 monotherapy treatment will be included in the summaries and listings of safety data. Overall safety profile will be characterized by type, frequency, severity, timing, duration, AEs’ relationship to study drug, laboratory abnormalities, and vital signs. All analyses will be descriptive. All AE data will be summarized separately for Parts 3 and 4 and also combined (Parts 3 and 4).

Baseline values are defined as the last valid value prior to study drug administration. Baseline safety data will be presented along with subsequent safety values assessed during or after drug administration.

#### **9.3.3.1        Adverse Events**

Adverse events will be classified using the Medical Dictionary for Regulatory Activities (MedDRA) classification system and the severity of the toxicities will be graded according to the NCI CTCAE v 5.0. Adverse event data will be summarized separately for Parts 3 and 4 and also combined (Parts 3 and 4).

In all summaries, emphasis will be placed on TEAEs, namely, those with initial onset or those that worsen in severity after the first dose of MT-3724. Adverse events will be summarized by the frequency of subjects experiencing TEAEs corresponding to MedDRA System organ class and preferred term and by worst NCI CTCAE grade. Summaries will also be provided of treatment related TEAEs, namely, those judged by the investigator to be related or likely related to MT-3724.

Adverse events resulting in discontinuation of MT-3724 treatment or withdrawal from the study, Grade 3 or higher, SAEs, and deaths on-study will be tabulated.

### **9.3.3.2        Laboratory Tests**

Laboratory data will be summarized for the observed values at each scheduled assessment, together with the corresponding changes from baseline using descriptive statistics.

For those analytes with CTCAE version 5.0 severity criteria specified, abnormal laboratory values will be summarized by shift tables displaying numerical values and percentages classified by baseline grade and maximum grade on treatment.

All laboratory data will be presented in data listings.

### **9.3.3.3        Vital Signs and Physical Examination Findings**

Vital signs data will be summarized by the observed values at each scheduled assessment, together with the corresponding changes from baseline using descriptive statistics.

Physical examination findings will be presented in data listings.

### **9.3.4        Other Analyses**

#### **9.3.4.1        Pharmacokinetic Analysis**

Pharmacokinetics data will be summarized separately for Part 3 and Part 4. The PK parameters will be estimated using standard noncompartmental methods as data permit. Pharmacokinetics parameters, where calculable, include:  $C_{max}$ ,  $t_{max}$ ,  $AUC_{0-4}$ ,  $AUC_{0-inf}$ ,  $AUC_{last}$ ,  $t_{1/2}$ ,  $V_z$ , and  $CL$ . Actual sample collection times will be used rather than scheduled collection times. Serum concentrations below the limit of quantification will be treated as 0. Embedded missing serum concentrations (ie, missing values between 2 observed values) will be estimated using linear extrapolation. This is consistent with using the trapezoidal rule to calculate AUC. Other missing serum concentrations will be excluded from calculations to estimate PK parameters.

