**Table 1-2. Schedule of Pharmacokinetic Samples**

	Time Points Relative to Dosing								Notes	
	Predose	During Infusion	After EOI							
	Within 4 h Prior SOI	10 m Before EOI	5 m	0.5 h	1 h	2 h	3 h	4 h		
Window			± 1 m	± 5 m	± 5 m	± 5 m	± 10 m	± 10 m		
Part 3										
C1D1	X	X	X	X	X	X	X	X	If an MT-3724 dose is rescheduled, then the PK samples planned per protocol for that dose should be drawn on the new dosing day. For example, if Dose 6 is delayed from D12 to D14, then the PK samples planned for D12 should be drawn on D14. Unscheduled assessments may be performed at any time at the investigator's discretion.	
C1D3	X	X	X	X	X	X				
C1D12	X	X	X	X	X	X				
CXD1	X	X	X							
Part 4										
C1D1	X	X	X	X	X	X	X		Samples for PK must be drawn from a different line than that used for MT-3724 administration.	
C1D3	X	X	X			X				
C1D12	X	X	X			X				
CXD1	X	X	X							

C = cycle; D = day; PK = pharmacokinetics, SOI = start of infusion; EOI = end of infusion.

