##### **6.1.1.3 Dose Schedule**

All doses of MT-3724 will be administered as IV infusion over 1 hour (window = 54 to 75 minutes) in a 21-day cycle according to the schedule specified in each cohort ([Table 6-1](#)).

NOTE: Each dose of MT-3724 must be preceded by premedication administered within 60 minutes before the start of each infusion (see [Section 6.1.2](#))

All doses should be administered within the first 16 days of the 21-day cycle. For Cycle 1 and 2 doses are preferably administered on Days 1, 3, 5, 8, 10, and 12 ( $\pm 1$  d). For Cycle 3 and later doses are preferably administered on Days 1, 8, and 15. All cycles should use the following guidelines:

- The first 3 doses of Cycle 1 must be administered at least 2 days (approximately 48 hours) apart.
- All subsequent doses must be at least 20 hours apart (more than 5 half-lives of MT-3724 in serum), and must not be administered on more than 2 consecutive days.

The first dose of the first cycle will require approximately 5 hours in the clinic which include approximately 4 hours of post-dose safety assessments. Subsequent doses will require approximately 3 hours in the clinic which include approximately 2 hours of safety assessments post-dose (see also [Section 1.3, Schedule of Activities \(SoA\)](#)).

No more than 14 days should elapse between cycles. If more than 14 days elapse, the investigator must consult with the medical monitor before initiating the next cycle of treatment. Refer to [Section 6.2](#) for dose modification guidelines and management of toxicities.

Treatment will continue until death, disease progression, unacceptable toxicity, withdrawal of consent, or another reason for withdrawal, or until study discontinuation.

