Schedule of activities: Table 1-1	
 
• Added ECG at EoT
 
• Added Chemistry and removed coagulation at STFU
 
• Added samples missing from screening: complement, histamine, immunoglobulins, cytokines, B-cells and immunophenotype, and MT-3724 ADA/NAb and removed concomitant medication review during screening
 
• Provided clarification on how prior systemic therapy should be recorded
 
• Provided clarification that the safety calls are not required for subjects dosed on weekly schedule
 
• Provided clarification regarding radiological exams for subjects who continue to receive MT-3724 beyond progression and that they are every 6 weeks starting from C1D1
 
• Reworked note for triplicate ECGs for clarification
 

Section	Revision Made
	
 
Changed that subject has to have rested quietly from 5 to 10 minutes to at least 5 minutes.
 
Updated footnotes to match protocol text and provide clarification on Day 15 visit
 
Updated requirement to change dose if body weight changes from > 10% to <math>\geq</math> 10%
 
Pregnancy test moved from central lab to local lab to allow for real-time assessment
 

Schedule of activities Table 1-2	
 
Removed PK samples from C1D3 and C1D12 at both the 0.5 h- and 1 h-after end of infusion timepoints for subjects in Part 4
 
Added “within” to “4 hr prior to SOI” to clarify that the PK samples can be drawn within 4 hours prior to SOI and not at 4 hr prior to SOI
 

Synopsis, Number of subjects	
 
Removed “who have received at least 2 standard of care systemic NHL treatment regimens (including anti-CD20 antibody therapy) will be enrolled” to avoid redundancy
 

Synopsis, Sections 3.1, 3.2 and 8.7.1	
 
Provided clarification that immunoglobulins are collected as pharmacodynamic endpoints
 

Synopsis; Section 4.1.3	
 
Removed “Safety” from Long Term Safety follow-up since LTFU visits are not done for safety; and also removed “Visits may occur by telephone contact when radiology data can be obtained from medical records” as it was less clear than what is stated in the section on LTFU (Section 8.1.5)
 

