Figure 3: Extended Access Schematic.....	21

LIST OF ABBREVIATIONS AND DEFINITION OF TERMS

Abbreviation	Definition
AE	Adverse event
ALT	Alanine transaminase
ANC	Absolute neutrophil count
AST	Aspartate transaminase
ATC	Anatomical therapeutic chemical
AUC	Area under the concentration versus time curve
AUC ₀₋₄	Area under the concentration versus time curve from time 0 to the end of the dosing interval 4 hours later, calculated using linear trapezoid rule
β-HCG	Beta human chorionic gonadotropin
BLQ	Below the limit of quantification
BSA	Body surface area
BUN	Blood urea nitrogen
C	Celsius
C _{max}	Maximum serum concentration
C _{min}	Trough serum concentration, taken 24 hours after dose and prior to subsequent dose
CBC	Complete blood count
CI	Confidence interval
CK	Creatine kinase
CL	Clearance
cm	Centimeter
CNS	Central nervous system
CO ₂	Carbon dioxide
CR	Complete remission
CRu	CR/unconfirmed
CSR	Clinical study report
CT	Computed tomography
CTCAE	Common Terminology Criteria for Adverse Events
dL	Deciliter
DLCO	Diffusion capacity of carbon dioxide
DLT	Dose-limiting toxicity
DNA	Deoxyribonucleic acid
DOA	Duration of response
ECG	Electrocardiogram
ECOG	Eastern Cooperative Oncology Group
eCRF	Electronic Case Report Form
EE	Efficacy-evaluable

Abbreviation	Definition
EEG	Electroencephalography
FDA	Food and Drug Administration
FEV ₁	Forced expiratory volume in 1 second
g	Gram
GGT	Gamma glutamyl transferase
ICH	International Conference on Harmonisation
IEC	Independent Ethics Committee
IRB	Institutional Review Board
ITT	Intent-to-treat
IWG	International Working Group
IV	Intravenous
kg	Kilogram
L	Liter
LDH	Lactic dehydrogenase
m ²	Square meter
MCH	Mean corpuscular hemoglobin
MCHC	Mean corpuscular hemoglobin concentration
MCV	Mean corpuscular volume
MedDRA	Medical Dictionary for Regulatory Activities
mEq	Milliequivalence
mg	Milligram
mL	Milliliter
mm	Millimeter
mm ³	Cubic millimeter
Msec	Millisecond
MTD	Maximum tolerated dose
µL	Microliter
N	Number
NCI	National Cancer Institute
ORR	Objective response rate
OS	Overall survival
PASS	Power and Sample Size
PD	Progressive disease
PDn	Pharmacodynamic
%	Percent
PET	Positron emission tomography
PFS	Progression-free survival
PFT	Pulmonary function test
pH	Hydrogen ion concentration

Abbreviation	Definition
PK	Pharmacokinetic
PR	Partial remission
PT	Preferred term
PTT	Partial thromboplastin time
QT	Interval between Q and T waves
QTc	Corrected interval between Q and T waves
RBC	Red blood cell (count)

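### The straight-line AUC and gap-filling rules in Protocol 9.3.4.1 raise AUC on the thinly sampled Part 4 C1D3 and C1D12 profiles relative to densely sampled ones; the size depends on an unstated half-life, and the fix is cheap

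*Protocol*

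**What the plan says.** Protocol Section 9.3.4.1 sets the general method: "The PK parameters will be estimated using standard noncompartmental methods as data permit". A concentration missing between two observed values "will be estimated using linear extrapolation. This is consistent with using the trapezoidal rule to calculate AUC". The operation described is interpolation, although the text calls it extrapolation. The next rule reads "Other missing serum concentrations will be excluded from calculations to estimate PK parameters". Only the other missing values are excluded, so as written the filled values enter every PK parameter, half-life included. No log-down rule is given, and no rule for choosing the points of the terminal slope.

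The explicit wording "calculated using linear trapezoid rule" appears only in the SAP's list of abbreviations, under AUC0-4. That SAP is based on protocol v7.0, covers Parts 1 and 2 and the extension study, and defers PK analysis to a separate document.

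Protocol Table 1-2 ("Schedule of Pharmacokinetic Samples") gives these post-infusion times:

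| Day | Part 3, after EOI | Part 4, after EOI |
|---|---|---|
| C1D1 | 5 min, 0.5, 1, 2, 3, 4 h | 5 min, 0.5, 1, 2, 3 h |
| C1D3, C1D12 | 5 min, 0.5, 1, 2 h | 5 min, 2 h |

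Each of these days also has a predose sample and one 10 min before EOI. The version 10 entry in Section 12 agrees with the current table and shows that the thinning was intended: "Removed PK samples from C1D3 and C1D12 at both the 0.5 h- and 1 h-after end of infusion timepoints for subjects in Part 4".

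**The concern.** After a 1-h infusion the concentration falls roughly exponentially. A straight line between two points on such a curve lies above it, and the excess grows with the gap measured in half-lives. The gap is 1 h 55 min on Part 4 C1D3 and C1D12. On Part 3 C1D3/C1D12, and on C1D1 in both Parts, the same stretch is split into three shorter steps. Identical kinetics therefore give different computed AUCs purely because of the schedule.

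Protocol Section 8.6 gives single-dose and repeat-dose PK as the purpose of sampling. In Part 4 that sets a dense C1D1 profile beside sparse C1D3 and C1D12 profiles. Under Table 6-1, C1D3 is given at the same µg/kg dose as C1D1, while C1D12 is given at a higher one. Dose-normalising C1D12 would not remove the effect, because the artefact is a ratio that does not depend on dose.

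A second issue is that a value filled on a straight line sits above the log-linear decline. If it is used in the terminal-slope regression, it distorts the half-life.

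**Working it through.** The documents state no AUC, half-life or bias figure for MT-3724, so there is nothing to reproduce first.

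**Inputs**
- Infusion of 1 h (Protocol 6.1.1.3).
- Sampling times from Table 1-2, in hours from start of infusion. Sparse (Part 4 C1D3/C1D12): 0, 0.833, 1.083, 3. Dense (Part 3 C1D3/C1D12): 0, 0.833, 1.083, 1.5, 2, 3. Part 4 C1D1 shares the dense times up to 3 h.
- Half-life: Section 6.1.1.3 says 20 h is more than 5 half-lives, so t1/2 < 20/5 = 4 h. No point value is given. Assumed range: 0.5 to 4 h.
- Assumed model: one compartment, mono-exponential decline, no noise, no carry-over.

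**Formulas**, with k = ln 2 / t1/2 and concentration in units of infusion rate / CL:
- C(t) = 1 − e^(−kt) for t ≤ 1; C(t) = (1 − e^(−k)) e^(−k(t−1)) for t > 1.
- Linear step: Δt (C1 + C2)/2. Log step: Δt (C1 − C2)/ln(C1/C2).

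**Worked case, t1/2 = 1 h.** C = 0.4388, 0.4719, 0.3536, 0.2500, 0.1250 at 0.833, 1.083, 1.5, 2, 3 h.
- Sparse, linear: 0.1828 + 0.1138 + 0.5721 = 0.8687.
- Dense, linear: 0.1828 + 0.1138 + 0.1720 + 0.1509 + 0.1875 = 0.8070.
- True AUC 0–3 h: 0.2787 (infusion) + 0.5410 (decline) = 0.8197.
- Sparse/dense = 0.8687/0.8070 = 1.076.
- Sparse, log-down: 0.1828 + 0.1138 + 0.5005 = 0.7971, which is −2.7% against the true value. Dense gives the same, because a log step is exact on a mono-exponential.

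**AUC 0–3 h from start of infusion**

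| t1/2 (h) | Sparse, linear: bias | Dense, linear: bias | Sparse/dense, linear | Sparse/dense, log-down | Log-down bias, both |
|---|---|---|---|---|---|
| 0.5 | +18.0% | −3.8% | 1.226 | 1.000 | −6.6% |
| 1 | +6.0% | −1.5% | 1.076 | 1.000 | −2.7% |
| 2 | +1.2% | −0.9% | 1.022 | 1.000 | −1.3% |
| 4 | −0.1% | −0.6% | 1.006 | 1.000 | −0.7% |

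The ratio column applies equally to Part 4 C1D12 against Part 4 C1D1 over 0–3 h, at equal or normalised dose. On C1D1 the two Parts differ by at most about 0.25 percentage points of bias.

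**Filled values.** A missing 1-h sample filled linearly between 0.5 h and 2 h is too high by 42%, 11%, 2.9% and 0.7% at the four half-lives. On the Part 3 C1D12 schedule the resulting half-life error is between −3.5% and +1.3%, depending on half-life and fit window. Across other missing samples and windows at t1/2 = 1 h it ranges from −14% to +4%; at 4 h, from −4% to +1%. It is exactly zero when the filled point is the centre of three equally spaced points. Linear filling leaves a linear-trapezoid AUC unchanged compared with skipping the point.

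**The case against.** Several points on the other side stand.

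- **The AUC rule is partly inferred.** For Parts 3 and 4 the protocol names only the trapezoidal rule; linear describes the fill. The inference is reasonable, because a straight-line fill matches only the linear trapezoid, but it remains an inference.
- **Materiality is not shown.** With the half-life only bounded below 4 h, the effect could be under 1%. At 4 h the sparse linear profile is closer to the truth than the dense one.
- **No contrast is planned.** Section 9.3.4.1 summarises the Parts separately, and no objective names accumulation, dose-proportionality or a Part 3 versus Part 4 comparison. A reader might infer that the artefact would show up as accumulation in Part 4. By AUClast it mostly would not: C1D12 sampling stops 2 h after EOI and C1D1 at 3 h, so at equal dose and kinetics the linear AUClast ratio C1D12/C1D1 is 1.19, 0.96, 0.84 and 0.78 at 0.5, 1, 2 and 4 h. From 1 h upward, truncation outweighs the trapezoid error.
- **Exposure-response.** A reader might also infer that the bias passes into that model. Section 9.3.4.2 places it in a separate analysis plan, and nothing says it will use these AUCs.
- **Half-life.** Part 4 C1D3 and C1D12 have only two post-infusion samples, so a conventional three-point fit is not possible there. The protocol already limits parameters to what the data permit. The distortion needs a lost embedded sample on another profile, and a filled point used in the fit.
- **Log-down has a cost.** Its underestimate on dense profiles is somewhat larger than the linear rule's (−2.7% against −1.5% at 1 h). Exact agreement between schedules also relies on mono-exponential decline: under illustrative bi-exponential declines (assumed, for example 0.25 h and 2 h phases) log-down left sparse/dense ratios of 1.05 to 1.12, still smaller than under the linear rule.

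**Conclusion.** The point holds as a low-priority improvement to a descriptive secondary analysis. Combined with Table 1-2, the straight-line rules raise AUC on Part 4 C1D3 and C1D12 relative to dense profiles over the same 3 h. The shift is about 23%, 8%, 2% or 0.6% for assumed half-lives of 0.5, 1, 2 or 4 h under a one-compartment model. It is a relative shift: in absolute terms the sparse profile is clearly too high only at short half-lives. C1D1 is essentially unaffected between Parts. The practical relevance is single-dose against repeat-dose PK within Part 4. The half-life limb is weaker, mostly a few percent and of varying sign, and it rests on filled values being used in the slope fit, which the text implies but does not state. The documents do not support a claim that the plan would report false accumulation or a false difference between Parts. The primary ORR analysis is unaffected.

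**What to change.** In Protocol 9.3.4.1 and the PK analysis document:

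1. Name the AUC rule as linear-up/log-down: linear while concentrations rise, logarithmic once they fall after EOI.
2. Do not fill embedded missing concentrations; let the log step span the gap. If filling is kept, do it on the log scale and call it interpolation.
3. Fit the terminal slope to observed quantifiable points only.
4. Where days or Parts are set side by side, use a common interval, such as start of infusion to 2 h after EOI, rather than AUClast.

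The cost is a few sentences and one software setting, with no new samples. The accepted downside is a shared underestimate from the infusion phase and the unsampled peak at EOI, −0.7% to −6.6% for half-lives from 4 down to 0.5 h. Because it is the same on both schedules under mono-exponential decline, it does not disturb comparisons. The sponsor can settle how much this matters from any half-life estimates it holds from Parts 1 and 2.

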### 9.3.4.2 Pharmacodynamic Analysis

B-cell count and immunophenotyping results obtained by flow cytometry will be presented as absolute values and percentage change from pre- to post-dose time points. The absolute values and changes from baseline by time point during the treatment will be tabulated and plotted for the pharmacodynamic analysis set.

Details of the descriptive statistical analyses of pharmacodynamic data will be provided in a separate statistical analysis plan. Pharmacodynamic data will be summarized separately for Part 3 and Part 4.

The details of the exposure-response modeling analysis will be described in a separate Modelling and Simulation (M&S) Analysis Plan and the results will be presented in a separate M&S report.

### 9.3.4.3 Immunogenicity Analysis

Data for the ADA against MT-3724 will be obtained. The ADA titer will be determined for ADA samples confirmed as a positive result. The data for the NAb against MT-3724 will be reported as positive or negative. These data will be summarized separately for Part 3 and Part 4.

The number and percent of subjects with a detectable ADA titer, and separately with a positive NAb result, will be summarized by time point for each treatment group/cohort. The individual subject's ADA and NAb results will be listed by time point during the treatment; the listings will be presented for the pharmacodynamic analysis set. The individual subject's ADA titer will be plotted by time point during the treatment.

Details of the descriptive statistical analyses of immunogenicity data will be provided in a separate statistical analysis plan.

## 9.4 Data Safety Monitoring Board

A Data Safety Monitoring Board (DSMB) will be established to monitor and evaluate the safety of subjects on an ongoing basis and to maintain oversight of the study data and monitoring process. The committee will consist of at least 1 independent experienced oncologist, statistician, and pharmacovigilance physician, the sponsor and its representatives and any other person the study team considers necessary to assist with study decisions. The committee will meet prior to starting Part 4, and according to the DSMB Charter established at the beginning of the trial. The DSMB will meet periodically during the expansion cohort. The DSMB will meet to discuss the overall incidence of serious related AEs (SAEs and AEs with CTCAE Grade 3 or 4) and Adverse Events of Special Interest to ensure that subject safety is addressed appropriately. The sponsor has the discretion to suspend enrollment for safety or efficacy reasons at any time pending DSMB review. The DSMB will also meet at unscheduled times according to clinical necessity. All SAEs and suspected Adverse Events of Special Interests will be reported to the DSMB by the

Compound: MT-3724  
Protocol MT-3724\_NHL\_001  
Protocol Date and Version: 12 February 2021, v11.0

sponsor in accordance with regulatory timelines. Refer to the DSMB Charter for additional details.

### 10.1.2 Regulatory and Ethical Considerations

The procedures set out in this study protocol, pertaining to the conduct, evaluation, and documentation of this study, are designed to ensure that the sponsor, its authorized representative and investigators abide by Good Clinical Practice (GCP) as described in International Conference on Harmonisation (ICH) guideline E6 ([ICH, 2016](#)), and in 21 Code of Federal Regulations (CFR) Parts 50, 54, 56, and 312. Compliance with these regulations also constitutes compliance with the ethical principles described in the most recent revision of the Declaration of Helsinki ([WMA, 2013](#)) that is recognized by the US Food and Drug Administration (US FDA) and the European Medicines Agency.

The investigator should ensure that all persons assisting with the trial are adequately qualified, informed about the protocol, any amendments to the protocol, the study treatments, and their trial-related duties and functions. The investigator should maintain a list of sub-investigators and other appropriately qualified persons to whom significant trial-related duties have been delegated.

Prior to initiation, the principal investigator will submit the study protocol, Investigator's brochure, sample ICF, and any other documents that pertain to subject information, recruitment methods and advertisements, to the Institutional Review Board (IRB)/Independent Ethics Committee (IEC). The principal investigator must also submit any other information that may be requested to the IRB/IEC for review and approval. Each investigator's IRB/IEC will review these materials in accordance with GCP guidelines. The investigator will request that the IRB/IEC provide written approval and will keep on file records of initial study approval.

After approval by the committee, the following documentation will be sent to the study manager before the study commences:

- Confirmation of IRB/IEC approval of the protocol.
- Confirmation of IRB/IEC approval of the ICF and applicable addenda.
- A list of IRB/IEC members, their representative capacity, and their affiliation (a current Health and Human Services General Assurance number will suffice).

The investigator must submit and, where necessary, obtain approval from the IRB/IEC for all subsequent protocol amendments and changes to the ICF provided by Molecular Templates or its agents. The investigator may not make changes to this protocol without Molecular Templates agreement.

The investigator must conduct the study according to the most recent, approved protocol version. For deviations, the investigator or designee must document and explain any deviation from the protocol. The investigator should also notify the IRB/IEC of deviations from the protocol or SAE occurring at the site as per the IRB/IEC standard operating procedure, as well as other AE reports received from Molecular Templates or its representative and provided to the investigator, in accordance with local procedures.

The principal investigator will be responsible for obtaining annual IRB/IEC approval or renewal throughout the duration of the study. Copies of the investigator's reports and the IRB/IEC continuance of approval must be sent to Molecular Templates' representative.

